#### 9.3.4.2 Concurrent Use of Other Acting Medications

In addition of the assessment of individual medications listed in Annex 3, the following groups of medications and ATC codes will be assessed at the start date and during follow-up as described above:

- Cardiovascular system – C
  - Antihypertensives – C02
  - Lipid-modifying agents – C10
- Drugs used in diabetes – A10
- Drugs for obstructive airway diseases – R03
- Non-steroidal anti-inflammatory drugs – M01A
- Antidepressants – N06A

 <http://medicine.iupui.edu/clinpharm/ddis/clinical-table/> (accessed February 2015)

<http://www.fda.gov/Drugs/DevelopmentApprovalProcess/DevelopmentResources/DrugInteractionsLabeling/ucm080499.htm> (accessed February 2015)

### **9.3.5 Concurrent Use of Selected Antithrombotic Agents**

In addition to potentially interacting drugs, the concurrent use of cilostazol with platelet aggregation inhibitors and antithrombotic agents will be assessed. Antithrombotic agents are listed in Table 5.

Use of each antithrombotic agent will be defined, similarly to cilostazol use, according to the days of supply of each prescription. If days of supply of prescriptions are not recorded in some databases, they will be estimated from descriptive analysis of the number of days between consecutive prescriptions. Current use of each antithrombotic agent is defined as the time involving the days of supply of each prescription plus 7 days to allow for a potential delay in the start of treatment.

Concurrent use of cilostazol and antithrombotic agents will be ascertained as follows:

- At the start date:
  - Use of antithrombotic agents at the start date will be ascertained according to the days of supply of the most recent prescription for each antithrombotic agent before the start date (date of first prescription for cilostazol).
- Overall:
  - Patients simultaneously contributing time to consecutive use of cilostazol and current use of antithrombotic agents at the start date and during follow-up.

### **Use of Platelet Aggregation Inhibitors**

New users of cilostazol who are concurrently treated with platelet aggregation inhibitors at the start date will be followed to assess the proportion of patients discontinuing the use of platelet aggregation inhibitors. Current use of platelet aggregation inhibitors at the start date will be assessed according to the days of supply of the most recent prescription before the start date. Days of supply of a prescription is defined as the number days of intended duration of treatment for that prescription. If days of supply of prescriptions for platelet aggregation inhibitors are not recorded in some databases, they will be estimated from descriptive analysis of the number of days between consecutive prescriptions.

Discontinuation of platelet aggregation inhibitors will be assessed during the time of consecutive use of cilostazol. Discontinuation is defined as any concurrent user of cilostazol and platelet aggregation inhibitors at the start date who does not have a recorded prescription for a platelet aggregation inhibitor after 60 days of ending the days of supply of the prior prescription. Sensitivity analyses for periods of 30 and 90 days after the end of the prior prescription will be conducted.

### **9.3.6 Baseline Characterisation of New Users for the Assessment of Planned Risk Minimisation Measures (SmPC Changes)**

New users of cilostazol will be characterised to evaluate the impact of the risk minimisation measures that Otsuka submitted to the EMA in October 2012. The risk minimisation measures include SmPC changes to identify a more restricted target population and to decrease the daily dose when cilostazol is used with potentially interacting medications. The risk minimisation measures also include communication initiatives to HCPs.

To evaluate the impact of the risk minimisation measures, a second DUS (DUS2) will be initiated 6 months after the implementation of the SmPC changes, and results will be compared with those obtained in the first DUS (DUS1).

The SmPC changes and the characteristics of users that will be evaluated in DUS1 and DUS2 are detailed in Table 7.

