## 8 Research Question and Objectives

The primary objectives of the DUS are as follows:

- To describe the characteristics of new users of cilostazol according to the following factors:
  - Demographics (e.g., age and sex)
  - Baseline comorbidity including conditions listed in the SmPC and the risk management plan (RMP) as potential or identified safety concerns (Otsuka Pharmaceutical Europe Ltd, 2012).
  - Baseline and concurrent use of medications potentially interacting with cilostazol and other medications

- Specific comorbidity and use of medications considered in the proposed risk minimisation measures, specifically those included in the proposed changes to the SmPC
- To describe the duration of the use of cilostazol and discontinuation patterns

Secondary objectives of the DUS are as follows:

- To quantify and describe off-label prescribing
- To describe dosage patterns of the use of cilostazol
- To assess the proportion of patients who are hospitalised for any cause while treated with cilostazol
- To describe the medical specialties of physicians prescribing cilostazol

The study objectives are the same for DUS1 and DUS2. DUS1 provides the baseline characteristics of users of cilostazol before the implementation of SmPC changes and communication with HCPs. DUS2 will be conducted after the implementation of these measures to evaluate their impact on the prescribing of cilostazol.

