### **9.7.5 Assessment of Changes to the Summary of Product Characteristics**

Analysis Tables 17, 18, and 26: The number and percentage of users by sex and age group (< 70 years, ≥ 70 years) will be calculated for the following conditions:

- Smoking: current, past, non-smoker (Analysis Table 17A)
- Number and percentage of users with at least one visit for any reason with a general practitioner or specialist between (a) 2 months and 4 months after the start date and (b) 1 month and 6 months after the start date, evaluated by the clinical review of a sample of patient profiles (Analysis Table 17B) and by diagnosis codes in all users (Analysis Table 17C). Analysis is restricted to patients who are current users of cilostazol at 3 months after the start date.
- Number and percentage of users with at least one visit for intermittent claudication with a general practitioner or specialist between (a) 2 months and 4 months after the start date and (b) 1 month and 6 months after the start date, evaluated by the clinical review of a sample of patient profiles (Analysis Table 17B) and by diagnosis codes in all users (Analysis Table 17C). Analysis is restricted to patients who are current users of cilostazol at 3 months after the start date.
- Discontinuation of cilostazol between 3 months and 4 months after the start date, evaluated using Kaplan-Meier survival curves (Analysis Table 17A and 26)

- Diagnosis within 6 months before the start date: unstable angina, myocardial infarction, or coronary intervention (Analysis Table 17A)
- Concurrent use of cilostazol and two or more platelet aggregation inhibitors (Analysis Table 17A)
- Reduction of daily dose of cilostazol from 200 mg to 100 mg among concurrent users of cilostazol and (a) potentially interacting medications (Analysis Table 18A) or (b) potent inhibitors of CYP3A4 or CYP2C19 (Analysis Table 18B) during continuous use of cilostazol

Analysis Table 19: Rates of visits to general practitioners and/or specialists among users at increased risk of serious cardiac events (patients with history of arrhythmias, coronary heart disease, or hypotension). Rates of visits per 100 person-years and 95% confidence intervals (CI) will be calculated for these patients and for those who are not considered at increased risk of serious cardiac events. Rate ratios and 95% CIs will be estimated comparing the rates in patients with increased risk with rates in patients without increased risk.

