### **9.7.8 Indications and Off-Label Use**

Analysis Table 21: The number and percentage of users by sex and age group (< 70 years, ≥ 70 years) will be calculated for each indication associated with the initiation of treatment according to the on-label and off-label use of cilostazol. The overall number, percentage, and 95% CI of patients prescribed according to the on-label and off-label use of cilostazol will be calculated by sex and age group (< 70 years, ≥ 70 years).

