Drug utilisation study with the objective of characterising users of cilostazol

Section 2: Source and study populations	Yes	No	N/A	Page Number(s)
2.1 Is the source population described?				8, 21
2.2 Is the planned study population defined in terms of: 2.2.1 Study time period? 2.2.2 Age and sex? 2.2.3 Country of origin? 2.2.4 Disease/indication? 2.2.5 Co-morbidity? 2.2.6 Seasonality?	     	     	     	21-22 8, 19-20 20-21 19-20 8-12, 19-20
2.3 Does the protocol define how the study population will be sampled from the source population? (e.g., event or inclusion/exclusion criteria)				22-23

Comments:

Section 3: Study design	Yes	No	N/A	Page Number(s)
3.1 Does the protocol specify the primary and secondary (if applicable) endpoint(s) to be investigated?				
3.2 Is the study design described? (e.g., cohort, case-control, randomised controlled trial, new or alternative design)				8, 20-21
3.3 Does the protocol describe the measure(s) of effect? (e.g., relative risk, odds ratio, deaths per 1000 person-years, absolute risk, excess risk, incidence rate ratio, hazard ratio, number needed to harm (NNH) per year)				
3.4 Is sample size considered?				8-12,44-45
3.5 Is statistical power calculated?				44-45

Comments:

Drug utilisation: no medication effect will be evaluated.

Section 4: Data sources	Yes	No	N/A	Page Number(s)

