7.3 Does the protocol address known effect modifiers? (e.g., collection of data on known effect modifiers, anticipated direction of effect)				
7.4 Does the protocol address other limitations?				49-50

Comments:

Assessment of confounders and effect modifiers does not apply as this is a drug utilisation study and no study endpoints are included. However, the study describes factors that are relevant to the use of medications such as comorbidity, comedications, age, and sex.

Section 8: Analysis plan	Yes	No	N/A	Page Number(s)
8.1 Does the plan include measurement of absolute effects?				
8.2 Is the choice of statistical techniques described?				
8.3 Are descriptive analyses included?				45-49
8.4 Are stratified analyses included?				45-49
8.5 Does the plan describe the methods for identifying: 8.5.1 Confounders?				
8.5.2 Effect modifiers?				
8.6 Does the plan describe how the analysis will address: 8.6.1 Confounding?				
8.6.2 Effect modification?				

Comments:

No measures of effect are estimated.

Section 9: Quality assurance, feasibility and reporting	Yes	No	N/A	Page Number(s)
9.1 Does the protocol provide information on data storage? (e.g., software and IT environment, database maintenance and anti-fraud protection, archiving)				45, 49
9.2 Are methods of quality assurance described?				49
9.3 Does the protocol describe quality issues related to the data source(s)?				49-50

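### The impact of the SmPC changes is to be judged by comparing DUS2 with DUS1, but the analysis plan gives no between-study difference and no interval for one

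*Protocol*

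**What the plan says.** Section 8 gives the second study an evaluative aim: "DUS2 will be conducted after the implementation of these measures to evaluate their impact on the prescribing of cilostazol". Section 9.3.6 names the means, a comparison in which DUS2 "results will be compared with those obtained in the first DUS (DUS1"). The Abstract says the same.

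Section 9.7 sets out the analysis by table:

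- **Tables 17, 18 and 26 (9.7.5):** "The number and percentage of users by sex and age group (< 70 years, ≥ 70 years) will be calculated for the following conditions". The list covers smoking, visits, discontinuation at 3 to 4 months (by Kaplan-Meier), recent cardiac diagnoses, two or more platelet aggregation inhibitors, and dose reduction.
- **Table 19 (9.7.5):** visit rates with intervals, and "Rate ratios and 95% CIs will be estimated comparing the rates in patients with increased risk with rates in patients without increased risk".
- **Table 28 (9.7.7):** number and percentage of users with contraindications new in 2013 and with those labelled earlier.
- **Table 21 (9.7.8):** "The overall number, percentage, and 95% CI of patients prescribed according to the on-label and off-label use of cilostazol".

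Annex 2 (checklist) marks the item on measures of effect and the item on choice of statistical techniques as not applicable. The comment on its analysis section reads "No measures of effect are estimated".

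**The concern.** The aim is a before-after judgement, but the planned output is two separate descriptions. No entry in Section 9.7 forms a DUS2 minus DUS1 difference or a ratio between the studies, and none attaches an interval to such a contrast. The intervals in Tables 19 and 21 do not fill the gap. One compares at-risk with other patients inside a study, and the other describes off-label use inside a study.

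The gap matters because DUS2 is a one-year cohort set against DUS1 cohorts gathered over roughly two to ten years. In the smaller databases a single percentage can move by a noticeable amount through sampling alone. Without an interval, a fall can be presented as impact and a rise as failure, and an unchanged figure can be presented as no effect when the data could not have shown one.

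**Working it through.** **1. The plan's own precision figures.** Table 11 gives binomial 95% limits for one percentage, with 1,500 to 8,000 users. Exact (Clopper-Pearson) limits match 49 of its 50 entries to one decimal. The exception is the lower limit at 1,500 users and 10%, which is 8.5 computed against 8.6 stated, a trivial gap. The table is sound for what it covers. At 1,500 users and 5% it gives 4.0 to 6.2, a half-width of (6.2 − 4.0)/2 = 1.1 points. It says nothing about the precision of a change between studies, or about cohorts below 1,500.

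**2. Size of DUS2.** Section 9.2.2.1 fixes 1 January to 31 December 2014. No expected number of new users is given, so the sizes below are an assumption: DUS1 users divided by DUS1 years (Tables 2 and 10; Section 9.4.2 for GePaRD).

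- THIN: 1,640 over June 2002 to December 2012, 10 + 7/12 years, gives about 155.
- SIDIAP: 3,375 over June 2009 to April 2012, 35/12 years, gives about 1,157.
- GePaRD: about 4,000 over 5 years gives 800.
- Sweden: 1,800 to 2,200 over 3.75 years gives 480 to 587.
- IACS: no count is given.

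**3. Precision of the difference.** DUS2 admits only first-ever users (Sections 9.2.3 and 9.2.5), so the two cohorts in a database do not overlap and can be treated as independent. With a common prevalence p,

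half-width = 1.96 × √[p(1 − p)(1/n₁ + 1/n₂)].

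At an assumed p = 0.05, p(1 − p) = 0.0475. For THIN:

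1.96 × √[0.0475 × (1/1,640 + 1/155)] = 1.96 × 0.0183 = 0.036, or 3.6 points.

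| Database | n₁ | n₂ (assumed) | Half-width at 5% |
|---|---|---|---|
| THIN | 1,640 | 100 / 155 / 300 | 4.4 / 3.6 / 2.7 points |
| SIDIAP | 3,375 | 1,157 | 1.5 points |
| GePaRD | 4,000 | 800 | 1.7 points |
| Sweden | 1,800 to 2,200 | 480 to 587 | 2.2 to 2.0 points |

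At 10% prevalence the THIN figures are 6.1 / 4.9 / 3.7 points.

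**4. What this means for reading bare percentages.** In THIN with 155 users the standard error is 1.83 points. A fall from 5% to 4%, one fifth in relative terms, is 1/1.83 = 0.55 standard errors. With no real change, a fall at least that large occurs by chance about 29% of the time.

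**5. The checklist against the text.** Annex 2 says no measure of effect is estimated, yet Section 9.7.5 plans rate ratios with intervals, and Sections 8 and 9.3.6 require a judgement of impact. These statements do not agree.

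**The case against.** The best reply is that Section 9.7 points to a separate DUS2 shell file, and the protocol refers to analysis plans; neither is shown. Interval methods and comparison columns often sit there. That is fair for the choice of method. It does not settle the point, because the protocol does not defer the contrast: its table-by-table plan omits it and its checklist marks effect measures not applicable.

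A second reply is that the checklist means only that no drug effect is studied, as its comment on study design indicates. That explains the wording and makes the inconsistency minor in itself. It does not supply the missing comparison.

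A third is that THIN is the least favourable database with a count. That stands: the half-widths in the other databases are about 1.5 to 2.2 points, and all rest on assumed accrual and prevalence.

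A reader might go further and infer that the plan must name one deciding measure, or that its many measures inflate a false-positive rate. The documents do not support either. The objectives are descriptive. The item "Does the protocol specify the primary and secondary (if applicable) endpoint(s) to be investigated" is marked not applicable, and no test or significance level is planned. Table 7 ties each label change to its own characterisation, so different movements across SmPC sections are a legitimate result. The visit measures overlap, since the 2 to 4 month window lies inside the 1 to 6 month window. Not every database holds every measure: smoking is only partly recorded (9.3.6), the Swedish registers lack visits to general practitioners, and GePaRD lacks dose information (both 9.4.2). An overall contraindication summary also already exists in Table 28.

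**Conclusion.** The point holds in this form: the protocol states that impact will be evaluated by comparing two studies, but plans no between-study contrast and no measure of its uncertainty, and its checklist denies that any effect measure is estimated. The consequence is largest in THIN, where the 95% half-width at 5% prevalence would be about 3.6 points (4.4 to 2.7 for 100 to 300 users), roughly three times the 1.1 points that Table 11 gives for a single percentage at 1,500 users. In SIDIAP it would be about 1.5 points. These sizes assume DUS1-average accrual in 2014 and illustrative prevalences; the protocol gives no DUS2 size, and use after the label change could be lower. The omission itself depends on none of these assumptions. It should be corrected, but it does not invalidate the descriptive results.

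**What to change.** In Sections 9.7.5 and 9.7.7, add a paragraph stating that:

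- for each SmPC-change measure available in a database, including the new-2013-contraindication summary in Table 28, the DUS2 minus DUS1 difference in proportions will be reported per database with a 95% confidence interval (for example Newcombe);
- for discontinuation, the difference will be taken between the Kaplan-Meier estimates, with an interval from their standard errors;
- for Table 19, the ratio of DUS2 to DUS1 visit rates will be given with a 95% confidence interval;
- impact will be read from these intervals.

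Correct the Annex 2 entries on measures of effect and statistical techniques to match.

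Naming Table 28 as the lead summary is optional. If that is done, note that Table 3 lists no procedure codes for SIDIAP, so coronary interventions may be under-recorded there, and that Section 9.9 says non-prescribed aspirin cannot be ascertained, which affects the count of platelet aggregation inhibitors.

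The cost is one paragraph and a few extra table columns. The proportion differences need only counts the two studies already tabulate; the discontinuation and visit-rate contrasts need the corresponding estimates and person-time. The one drawback for the sponsor is that fewer isolated shifts can be presented as evidence of impact.

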**Table 7. Proposed Changes in the Labelling of Cilostazol and Characterisation of Users**

Proposed Change to Summary of Product Characteristics	Characterisation in DUS
Restricted target population	
Indication	
4.1 Cilostazol is for second-line use in patients in whom life-style modifications (including smoking cessation and [supervised] exercise programmes) and other appropriate interventions have failed to sufficiently improve their intermittent claudication symptoms	Smoking status a
4.2 The physician should reassess the patient after 3 months of treatment with a view to discontinuing cilostazol where an inadequate effect is observed.	Number of patients seen by the treating physician after 3 months b Number of patients discontinuing after 3 months b
Contraindications	
4.3 Patients with unstable angina pectoris, myocardial infarction within the last 6 months, or a coronary intervention in the last 6 months	Unstable angina Myocardial infarction Coronary intervention
Patients treated concomitantly with two or more additional antiplatelet agents (e.g., aspirin, clopidogrel)	Concurrent use of two or more platelet-aggregation inhibitors
Other SmPC changes	
Warnings and precautions	
4.4 Based on its mechanism of action, cilostazol may induce tachycardia, palpitation, tachyarrhythmia, and/or hypotension. The increase in heart rate associated with cilostazol is approximately 5 to 7 beats per minute; in patients at risk, this may induce angina pectoris.	
Patients who may be at increased risk for serious cardiac adverse events as a result of increased heart rate, e.g., patients with stable coronary disease or a history of tachyarrhythmias, should be monitored closely during the treatment with cilostazol; the use of cilostazol in patients with unstable coronary disease or coronary intervention within the last 6 months is contraindicated (see SmPC Section 4.3).	Number of visits to general practitioner and/or specialist

Proposed Change to Summary of Product Characteristics	Characterisation in DUS
Posology	
4.2 Reduction of the dose to 50 mg twice daily is recommended in patients receiving medicines that strongly inhibit CYP3A4, e.g., several macrolides, azole antifungals, protease inhibitors, or medicines that strongly inhibit CYP2C19, e.g., omeprazole.	Daily dose

CYP = cytochrome P-450; DUS = drug utilisation study; SmPC = Summary of Product Characteristics.

  - Patients with a history of arrhythmias, hypotension, or coronary heart disease recorded at any time before the start date will be followed to assess the rates of visits to general practitioners or specialists. Visit rates for these patients will be used as a proxy of intensified monitoring and compared with the rates for the patients who do not have a history of arrhythmias, hypotension, or coronary heart disease.
- Posology
  - Daily dose of cilostazol at the start date will be assessed among concurrent users of potentially interacting medications at the start date
  - Reduction of daily dose to 50 mg will be assessed among patients who are prescribed a potentially interacting medication during continuous use of cilostazol.

The diagnosis, procedure, and medication codes that will be used to define the variables for the evaluation of the risk minimisation measures are included in Table 4 and Table 5.

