#### **9.2.5 Exclusion Criteria**

Because the DUS seeks to characterise all new users of cilostazol, no exclusion criteria regarding age, sex, or comorbidity will be applied.

Patients who have their first recorded prescription for cilostazol during the eligibility period (6 months of continuous enrolment in the database) will be excluded as they will not be new users at the start date. In addition, for DUS2, patients who have a recorded prescription for cilostazol at any time before the start will also be excluded.

Patients with records flagged as incomplete or as substandard data quality according to each database-specific quality-control measures will be excluded.

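### The at-risk group in Analysis Table 19 does not separate users with a recent coronary contraindication, so its DUS1–DUS2 visit rate mixes prescribing change with monitoring change

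*Protocol*

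**What the plan says.** Protocol Section 9.3.6, Table 7, quotes the SmPC 4.4 text that the visit analysis is meant to evaluate. Its key sentence has two parts. Patients at increased cardiac risk, for example "patients with stable coronary disease or a history of tachyarrhythmias, should be monitored closely during the treatment with cilostazol"; and, in the same sentence, "the use of cilostazol in patients with unstable coronary disease or coronary intervention within the last 6 months is contraindicated". The new SmPC 4.3 contraindication in the same table covers "Patients with unstable angina pectoris, myocardial infarction within the last 6 months, or a coronary intervention in the last 6 months".

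The list below Table 7 defines the analysed group: "Patients with a history of arrhythmias, hypotension, or coronary heart disease recorded at any time before the start date will be followed". It then gives the reading: "Visit rates for these patients will be used as a proxy of intensified monitoring". Section 9.7.5 specifies Analysis Table 19 as "Rates of visits to general practitioners and/or specialists among users at increased risk of serious cardiac events", with rates per 100 person-years and a rate ratio against users not at increased risk. It describes the group by the same three histories and removes nobody.

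Three other places complete the picture:

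- Section 9.2.5 states that "no exclusion criteria regarding age, sex, or comorbidity will be applied", so contraindicated users stay in the cohort.
- Section 9.3.6 says that the codes defining the "variables for the evaluation of the risk minimisation measures are included in Table 4 and Table 5". In Table 4, ischaemic heart disease is I20-I25, which contains unstable angina (I20.0) and acute myocardial infarction (I21). Coronary procedures are listed with it.
- Sections 8 and 9.3.6 make DUS1 the baseline and compare DUS2 with it to judge the measures.

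The look-back is not stated consistently. Section 9.1 assesses the conditions for warnings and precautions over the 6 months before the start date. Section 9.3.6, and the warnings item in the Abstract, use any time before it.

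**The concern.** Two of the measures under evaluation act on the same group of users. The contraindication is intended to stop cilostazol being started in people with recent unstable coronary disease. The warning is intended to increase the monitoring of those at risk who do receive it. Table 19 summarises both kinds of user in one visit rate and reads that rate as monitoring.

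The make-up of the group can therefore change between DUS1 and DUS2 because the contraindication is being followed. If recently unstable users are seen more often because of their coronary event, losing them lowers the average visit rate with no change in how anyone else is followed. A real gain in monitoring could then be understated, hidden or shown as a loss. Within a single phase, visits prompted by a recent coronary event would also count as intensified monitoring.

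**Working it through.** The protocol gives no visit rate, group share or precision target for Table 19, so there is no figure to reproduce. The check has two parts.

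**Membership.** A user with an infarction three months before the start date has coronary heart disease recorded before that date, so meets the Section 9.3.6 definition. The same user meets the new SmPC 4.3 contraindication. No exclusion in Section 9.2.5 and no restriction in Section 9.7.5 removes this user. The overlap is real. It rests on reading coronary heart disease as Table 4's ischaemic heart disease, a term match that the protocol leaves implicit.

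**Effect of a change in mix.** The inputs f and k are assumptions, not protocol figures:

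- f = share of the group's person-time in DUS1 contributed by users with a recent coronary contraindication
- k = their visit rate divided by that of the rest of the group
- r = visit rate of the rest, held equal in both phases

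DUS1 group rate = r × [(1 − f) + f × k]. DUS2 group rate after full removal = r. Relative change = 1 / [(1 − f) + f × k] − 1.

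Example: f = 10%, k = 2 gives 1 / (0.90 + 0.20) − 1 = 1 / 1.10 − 1 = −9.1%.

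| f | k=0.8 | k=1 | k=1.5 | k=2 | k=3 |
|---|---|---|---|---|---|
| 2% | +0.4% | 0 | −1.0% | −2.0% | −3.8% |
| 5% | +1.0% | 0 | −2.4% | −4.8% | −9.1% |
| 10% | +2.0% | 0 | −4.8% | −9.1% | −16.7% |
| 20% | +4.2% | 0 | −9.1% | −16.7% | −28.6% |

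If only half of these users are removed, f = 10% and k = 2 gives [(0.90 + 0.05 × 2) / 0.95] / 1.10 − 1 = −4.3%.

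The rate ratio moves by the same percentage if the comparison group's rate is unchanged.

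**Offset.** With full removal, the group rate stays level if monitoring of the rest rises by f × (k − 1): 2.5% at f = 5%, k = 1.5; 10% at f = 10%, k = 2; 20% at f = 10%, k = 3. A true 5% rise would appear as 1.05 / 1.025 − 1 = +2.4% in the first case and 1.05 / 1.10 − 1 = −4.5% in the second.

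**After separation.** In a row restricted to users without a recent coronary contraindication, the rate is r in both phases when monitoring is unchanged. The shift from removal is 0% for any f and k, and a true 5% rise shows as +5%.

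**The case against.** The strongest defence is that a broad group is legitimate. The SmPC sentence gives examples, not a closed list, and someone prescribed cilostazol despite a recent coronary event is certainly at increased cardiac risk. How often that person is seen is worth knowing. This stands, and it is why the existing Table 19 rows should be kept.

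A second defence is that much of the information is already reported. Analysis Table 17A counts the three coronary conditions within 6 months, and Analysis Table 28 counts new and older contraindications, so a fall in such users would be visible. The specified rate ratio is also within phase, and the comparison of DUS2 with DUS1 has no test or decision rule. This stands in part. Those tables give the number of contraindicated users but not their visit rates, so they cannot show how much of a change in Table 19 is due to mix.

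A reader might infer more than the protocol supports, in three ways:

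- That the rate will fall and monitoring will appear to worsen if the contraindication works. The direction depends on k exceeding 1 and on too small an offset. That is plausible after a recent coronary event, but no figure in the protocol shows it. At k = 0.8 the rate would rise.
- That ventricular arrhythmias add to the shift. Section 9.3.6 and the Abstract treat them as contraindications already in the label and retained, so the new measure does not remove those users.
- That contraindicated arrhythmias could be carved out with existing flags. Analysis Table 20 in Section 9.7.6 lists only arrhythmias as a whole, and using it as an exclusion would remove the tachyarrhythmia patients whom the warning addresses.

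The any-time look-back also admits remote and chronic disease, which dilutes the 6-month subset and makes f smaller.

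**Conclusion.** The point holds as a conditional one. As written, the Table 19 group contains users with a recent coronary contraindication, and nothing in Section 9.7.5 separates their visit rate. A comparison of DUS2 with DUS1 therefore mixes a change in who is prescribed cilostazol with a change in how at-risk users are monitored.

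The size is unknown. For shares from 2% to 5% and visit ratios from 1.5 to 2, full removal shifts the rate by about −1% to −5%. A share of 10% with a ratio of 2 to 3 gives about −9% to −17%. These results assume constant monitoring of the rest, and for the rate ratio a constant comparison rate. The look-back conflict bears on the size: under the 6-month window of Section 9.1, f would probably be larger than under the any-time window of Section 9.3.6.

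This is a worthwhile, inexpensive improvement to interpretation. It does not show that Table 19 is invalid.

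**What to change.** In Sections 9.3.6 and 9.7.5, keep Analysis Table 19 as it is and add visit-rate and rate-ratio rows, with confidence intervals, for at-risk users in two strata: with, and without, unstable angina, myocardial infarction or coronary intervention in the 6 months before the start date. These conditions are already specified for Analysis Table 17A, so no new code list is needed. Produce the rows in both DUS1 and DUS2, and state that the monitoring comparison rests on the stratum without these conditions.

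Reconcile the look-back for the warnings-and-precautions conditions between Section 9.1, the Abstract and Section 9.3.6, and apply one definition in both phases.

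The cost is smaller strata, with wider intervals, particularly in the contraindicated stratum, and a re-run of one DUS1 table. Section 6.1 reports DUS1 as complete in THIN, IACS, SIDIAP and Sweden by 30 January 2015, with the final report including GePaRD planned for April 2015, so the re-run involves several research centres.
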